10.3 Stratification Factors

Randomization will be stratified based on the following factors:

- **Age at diagnosis:** <55, 55-65, >65
- **Maximum diameter of microcalcifications:** <2cms, 2-5cms, >5cms
- **DCIS nuclear grade:** I or II

We will collect whether the patient has had prior surgical excision for the index diagnosis; this variable will be used for subset analysis and not stratification.

10.4 Data Safety Monitoring Board (DSMB) Reporting

The COMET trial will be subject to bi-annual formal review at the Alliance Foundation DSMB meetings. At each meeting we will utilize a template report formulated for use in Alliance trials, with appropriate modifications for the COMET follow-up study.

10.5 Supplementary/Secondary Analysis Plans

Planned Analysis for PRO data: For analyses of PRO endpoints, we will use t-tests and ANOVA to compare unadjusted mean scores for health-related PRO measures at baseline. We will use linear mixed-effects models to assess change in these domains over time. Among women who are allocated to surgery, we will examine differences by surgery type (e.g., lumpectomy followed by radiation vs. unilateral mastectomy vs. bilateral mastectomy) and compare changes between these groups over time. In addition to baseline disease and socio-demographic data, information relating to other treatment (e.g., endocrine treatment, radiation) as well as co-morbidities will allow us to control for potential confounding by these factors. We will also analyze the decision-making, DCIS knowledge, and risk perception data at baseline and compare these domains between the surgery and AM groups. We plan to measure risk perceptions and knowledge again at 2 years and will assess change between the two time points in each group using t-tests (e.g., for continuous scores) and McNemar's test (e.g., proportion correctly perceiving their risk).

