2.3 Endpoints

2.3.1 Primary endpoint:

Proportion of new diagnoses of ipsilateral invasive breast cancer in surgery and AM arms at follow up of 2-years.

2.3.2 Secondary endpoints:

- Quality of life and psychosocial outcomes;
 - Health related QOL at baseline, 6 months, 1 year, annually year 2-6, biannually thereafter.
 - Anxiety/depression at baseline, 6 months, 1 year, annually year 2-6, biannually thereafter.
 - Coping at baseline
 - Intolerance of uncertainty at baseline and 2 years
- Clinical outcomes
 - Mastectomy rate at 2, 5, 7 and 10 years
 - Breast conservation rate at 2, 5, 7 and 10 years
 - Contralateral invasive breast cancer rate at 2, 5, 7 and 10 years
 - Overall survival and invasive breast cancer-specific survival at 2, 5, 7, and 10 years
 - Ipsilateral invasive breast cancer rate in surgery and AM arms at 5, 7 and 10 years

2.3.3 Exploratory endpoints:

- Breast MRI utilization at 2, 5, 7 and 10 years
- Breast biopsy rate at 2, 5, 7 and 10 years
- Radiation rate at 2, 5, 7 and 10 years
- Chemotherapy rate at 2, 5, 7 and 10 years
- Self-reported co-morbidity at baseline, 6 months, 1 year, annually year 2-6, biannually thereafter.
- Adherence to hormonal therapy at 6 months, 1 year, annually year 2-6, biannually thereafter.
- Health behavior/lifestyle factors at 6 months and 2 years
- Symptoms, pain, body image, sexual function at baseline, 6 months, 1 year, annually year 2-6, biannually thereafter.

- Quality of decision making at baseline and 2 years
- Decisional regret at 1 year, annually year 2-6, biannually thereafter.
- Knowledge and risk perceptions at baseline and 2 years
- Decisional conflict at baseline
- Financial burden at 6 months
- Employment status at baseline, 6 months, 1 year, annually year 2-6, biannually thereafter.
- Use of complementary therapies at 6 and 24 months

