6. STUDY ASSESSMENTS AND PROCEDURES

Close follow up of outcomes in each group is critical to the validity of the proposed comparisons. Following registration and consent at the initial clinic visit, baseline demographic information and data regarding clinical presentation will be collected. All clinical outcome data will be collected by a trained clinical research assistant who has received GCP and HIPAA training. All registered patients will be asked to complete the **baseline survey** on paper after they have been registered (but prior to being randomized), with the follow-up surveys completed at specified time-points (either on-line or on paper) (see Section 7.1.3 Patient-Reported Outcomes describing the procedures for survey data collection.) Once registered to the trial, patients will be randomized to one of the treatment arms within four weeks; the monitoring period will start on the date of registration.

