6.1.3 Patient Reported Outcomes

Survey instruments for the project have been carefully selected to provide the most relevant patient centered outcomes (see Section 1.3). Questionnaire packets will be completed at baseline, 6, 12, 24, 36, 48, 60, 72, 96, and 120 months; a gap year letter will be sent to participants at months 84 and 108 (the years when a survey packet is not being sent) from UNC PRO Core in the same way that they receive the survey packets (either by email or by mail). This patient-reported outcome data collection will be conducted using the PRO Core survey platform, which enables web-based questionnaire completion, automated email reminders, data entry of paper forms, and tracking of participant survey completion. Surveys will be available in English or in Spanish. Language preference for each participant will be noted in PRO Core at baseline and can be changed throughout the study. Detailed information (screenshots, etc.) about how to use PRO Core for this study is provided in the training slide deck. The baseline questionnaire will be completed on paper after the patient has registered for the study (but prior to randomization). It will be data-entered into PRO Core by the site study staff and a copy will be kept on file at the site. The baseline questionnaires should be uploaded to Pro-Core.

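### For the exploratory knowledge and risk-perception endpoints, Section 10.5 specifies an arm comparison only on pre-randomisation data; no between-arm contrast at 2 years is specified

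*Combined protocol and SAP*

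**What the plan says.** Section 2.3.3 lists "Knowledge and risk perceptions at baseline and 2 years" among the exploratory endpoints. Table 2 in Section 7 schedules the knowledge instruments and the risk-perception items at baseline and month 24.

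Section 10.5 gives two analyses for these domains:

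- At baseline: "We will also analyze the decision-making, DCIS knowledge, and risk perception data at baseline and compare these domains between the surgery and AM groups".
- At 2 years, after a second measurement, the plan "will assess change between the two time points in each group using t-tests" for continuous scores. For binary items such as correct risk perception it names McNemar's test.

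On the timing of the baseline survey, Section 6 places it after registration "but prior to being randomized". Section 6.1.3 agrees: "The baseline questionnaire will be completed on paper after the patient has registered for the study (but prior to randomization").

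**The concern.** A baseline survey completed before randomisation cannot be affected by allocation, so any arm difference in it is chance. It describes the sample but says nothing about the effect of assignment. By 2 years, patients have lived with their assigned management and an effect on knowledge or perceived risk is possible. There, the stated analysis looks at each arm alone.

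A within-arm test asks whether that arm's change differs from zero. It does not ask whether the two arms changed by different amounts, and two such tests side by side do not answer that question either. At stake is whether the trial can report a usable treatment contrast for these two outcomes. A reader given one significant and one non-significant within-arm result could also take the pair as evidence of an arm difference.

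**Working it through.** **1. Is the 2-year analysis within arm?** Two features of Section 10.5 say so. The wording applies the tests in each group. McNemar's test compares paired responses from the same people, so it can compare baseline with 2 years in one arm but cannot compare two independent arms.

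**2. Does other text supply the contrast?**

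| Place | What it offers | What is missing |
|---|---|---|
| Section 2, opening | Intention to compare PROs between arms | Any method; these domains |
| Section 10.2, subgroup paragraph | Hypothesis that PRO measures may depend on arm | Any 2-year contrast for these domains |
| Section 10.2, long-term outcomes | Longitudinal linear mixed models for PRO data | An arm term; a 2-year contrast; these domains |
| Section 10.5, mixed-model sentence | Change over time in the health-related PRO measures named just before it | An arm contrast; knowledge and risk perception, which come later with their own tests |

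None names a between-arm 2-year comparison for knowledge or risk perception.

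**3. Sample size to use for illustration.** The plan gives no sample size, SD or effect size for these scales. Its only sample-size figure is for the primary endpoint in Section 10.2 (both rates 0.10, margin 0.05, one-sided alpha 0.05, 80% power):

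n = (1.645 + 0.842)² × 2 × 0.10 × 0.90 / 0.05² ≈ 445.1, rounded up to 446 per arm.

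This reproduces the stated figure. It is borrowed below as an assumed evaluable number per arm, together with an SD of change of 1 and two-sided alpha 0.05.

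**4. Discordant within-arm results when the arms do not differ.** With the same true change d (in SD units) in both arms, each within-arm test has power

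pw = 1 − Φ(1.96 − d√446) + Φ(−1.96 − d√446).

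The arms are independent, so the chance that exactly one is significant is 2 × pw × (1 − pw).

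| True change d, both arms | pw | Exactly one arm significant |
|---|---|---|
| 0.05 SD | 0.184 | 30% |
| 0.093 SD | 0.502 | 50% (the maximum) |
| 0.10 SD | 0.560 | 49% |
| 0.15 SD | 0.886 | 20% |
| 0.20 SD | 0.988 | 2% |

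A direct between-arm test would be falsely significant 5% of the time in every row.

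**5. The reverse case.** Suppose the true changes are 0.2 SD in one arm and 0.4 SD in the other. Both within-arm tests are then significant with probability about 99%, so the p-values show nothing of the 0.2 SD difference. A direct comparison of change has standard error √(2/446) = 0.067 and detects that difference with power Φ(0.2/0.067 − 1.96) ≈ 85%. Its 80%-power detectable difference is (1.96 + 0.842) × 0.067 ≈ 0.19 SD. With 540 per arm (1,080/2, no dropout) the corresponding figures are 91% and 0.17 SD.

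**The case against.** Four points can be made for the plan.

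- **The endpoints are exploratory.** They carry no hypothesis, margin or power, and appear in neither the primary nor the secondary objectives. This stands, and it limits the importance of the point. It does not make two within-arm tests a comparison of arms.
- **The comparison may be made anyway.** A reader might infer that the randomised comparison will never be carried out. The documents do not support that: Section 2 states a general intention to compare PROs between arms, and Section 10.2 names mixed models for PRO data. What they support is that no such contrast is specified for these domains.
- **No invalid inference is written down.** Nothing in Section 10.5 says that an arm difference will be concluded from discordant p-values, and describing change within groups is legitimate. This stands. The defect is an omitted contrast; the misreading is a risk for those who interpret the results.
- **The baseline comparison is not stated to be a significance test.** The t-tests and ANOVA in Section 10.5 are for health-related PRO measures at baseline. For knowledge and risk perception the plan says only that it will "compare these domains between the surgery and AM groups", so a criticism of baseline significance testing in these domains would go beyond the text.

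It is also fair to say that discordance depends heavily on the true change. Quoting only values near 50% would select the worst part of the curve, since at 0.20 SD it is about 2%.

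**Conclusion.** The concern holds in a limited form. For knowledge and risk perception, the only arm comparison specified uses data collected before randomisation, and the only analysis specified for the 2-year data is within arm. As written, the method cannot deliver for these domains the between-arm PRO comparison that Section 2 sets out to make.

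Under the assumptions above, within-arm results disagree by chance in about 2% to 50% of trials for equal true changes of 0.20 down to 0.09 SD, and within-arm testing can also hide a real difference. These figures are illustrations of scale, not estimates for this trial. The textual finding does not depend on them. Primary and secondary conclusions are unaffected.

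**What to change.** In Section 10.5, make the 2-year analysis of these domains a between-arm comparison of patients as randomised:

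- **Continuous scores:** ANCOVA of the 2-year score on arm, baseline score and the stratification factors (age group, microcalcification diameter, nuclear grade). The protocol's own linear mixed model would serve equally well if it includes an arm-by-time term and the month-24 contrast is named.
- **Correct risk perception:** logistic regression of 2-year status on arm, baseline status and the stratification factors.
- **Reporting:** the arm difference or effect estimate with its 95% CI. Label within-arm change and the baseline arm comparison as descriptive only.

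The exact model is a matter of choice; any pre-specified between-arm estimate with a confidence interval would close the gap. The data are already scheduled at baseline and month 24, so the cost is a few sentences of SAP wording and minor analysis work.

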10.6 Duration of Follow-Up

Participants in both arms of the study will be followed for 10 years from time of registration. For the surgery and AM groups, required monitoring **years 1-5** consists of the following:

- Clinical examination including history and physical examination every 6 months.
- Unilateral mammography (MMG) of the affected breast every 12 months in the surgery arm; not required if patient has had mastectomy of the index breast.
- Unilateral mammography (MMG) of the affected breast every 6 months in the AM arm.
- MMG of the unaffected breast every 12 months; not required if patient has had mastectomy of the unaffected breast

After 5 years, participants in both arms will undergo physical examination and bilateral mammogram every 12 months; mammogram is not required if patient has had mastectomy of both the index and the unaffected breast (for additional information on required clinical follow-up (years 6-10), see Section 7.1.1.).

10.7 Survival Follow up

Any study participant can choose to withdraw from the study at any time for any reason, including no specified reason. Patients in the surgery arm cannot opt for the AM arm after surgery, but in the event that a patient withdraws from the study, the date of withdrawal and reason for withdrawal will be recorded. The patient will be censored in time-to-event analyses at the date of withdrawal from the study

Patients in the AM arm may choose to either withdraw from the study or opt to proceed with surgery at any time. In the event that a patient in the AM arm opts to proceed with surgery in the absence of invasive progression, the date of withdrawal and reason for withdrawal will be recorded. As for the surgery arm, in the event that a patient withdraws from the study, the patient will be censored at the date of withdrawal from the study.

Patients in the AM arm with progression to invasive breast cancer are required by the study protocol to proceed with surgery for their invasive breast cancer. Patients who have invasive breast progression and do not wish to have surgery will continue to remain in follow up with their invasive cancer event recorded, at the time of invasive breast progression for the primary analysis. For further exploratory analyses, the lack of surgery for these patients will be recorded.

For patients who choose to no longer be followed per the protocol schedule, the patient can choose to enter the Survival Follow-up Phase. Survival data, ongoing adjuvant therapies and subsequent disease progression data will be collected during this phase of the study every 12 months for 10 years from registration. Telephone contact is acceptable as well as medical record review.

Follow-up will be discontinued early due to:

- Patient Death
- Patient Withdrawal of consent for all follow-up
- Patient deemed lost to follow-up

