5.2.2 Treatment

5.2.2.1 Surgery

Patients in the Active Monitoring arm will not undergo primary surgery and will only undergo surgery if there is documentation of invasive breast progression requiring surgical intervention. If the patient opts for surgery in the absence of invasive breast progression, they will be considered as having declined the arm to which they were specifically randomized (see Section 11.2); in this case they will be offered an option to continue to complete follow-up.

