10.2 Sample Size, Accrual Time and Study Duration

Power and Sample Size Considerations. Sample size for this study was estimated using a 2-group test of non-inferiority of proportions, with the 2-year invasive breast cancer rate in the surgery group assumed to be 0.10 based on published studies.^{61,62} The non-inferiority margin assumed was 0.05. Based on a 1-sided un-pooled z-test, with alpha=0.05, a sample size of n=446 per group will have 80% power⁶⁴ to detect the specified non-inferiority margin. The proportion of patients who decline the arm to which they are specifically randomized can diminish the estimate of treatment difference, and could also widen the confidence bounds, but the analytical approaches proposed here aim to diminish the impact on bias of the treatment difference. With a 3-year duration of accrual and 2 additional years of follow-up, we anticipate approximately 148 total events.

Analysis of Primary Outcome (See below for outcomes definitions). This trial was designed anticipating non-acceptance of arm allocation, and the proportion of patients that do not accept their arm allocation can lead to bias in estimates of treatment differences. Thus, we plan to complete several analyses of the primary outcome, reporting the primary intent to treat (ITT) analysis as well as sensitivity analyses that are intended to reduce the bias in estimation of treatment difference in this setting.

We assume that a clinically acceptable difference in 2-year invasive cancer diagnosis rate in order to conclude non-inferiority is 5%. Cumulative incidence curves will be used to estimate the invasive cancer diagnosis rates over time, and at the 2-year point, the difference in rates will be estimated and a 1-sided upper confidence bound of (AM-GCC) will be computed, using methods described by Austin.⁶⁵ We will conclude that AM is not inferior to Surgery if the upper confidence bound on the risk difference at 2 years is less than 5%.

ITT Analysis. The ITT analysis of 2-year invasive cancer diagnosis rate will be conducted using all patients, as randomized, and will be completed using Kaplan-Meier estimates, stratified by group, combined with the Greenwood's confidence interval. The difference in invasive cancer risks will be computed from the Cox model with treatment at 2 years, with a 1-sided 95% confidence interval of the difference (AM-GCC) computed.

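### Section 10.7 leaves unclear whether AM women who choose surgery without invasive progression are censored; read literally, it conflicts with the ITT plan and can bias the AM estimate in either direction

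*Combined protocol and SAP*

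**What the plan says.** Section 10.7 opens its AM paragraph with two separate choices: "Patients in the AM arm may choose to either withdraw from the study or opt to proceed with surgery at any time". It then says that when such a woman "opts to proceed with surgery in the absence of invasive progression, the date of withdrawal and reason for withdrawal will be recorded". The paragraph ends with the censoring rule: for anyone who withdraws from the study, "the patient will be censored at the date of withdrawal from the study". The preceding paragraph, on the surgery arm, uses the same withdrawal-date wording for true study withdrawal and attaches censoring to it. The list that closes 10.7 gives three reasons to end follow-up: death, loss to follow-up and "Patient Withdrawal of consent for all follow-up". Elective surgery is not among them.

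Other sections describe the same women differently:

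- **5.2.2.1** regards them as having declined their randomized arm and adds that "in this case they will be offered an option to continue to complete follow-up". It points to Section 11.2, which deals with regulatory and ethical compliance and does not mention the subject.
- **6.1.2** calls the decision a change in management, to be recorded with its reason.
- **10.2** anticipates it: "The proportion of patients who decline the arm to which they are specifically randomized can diminish the estimate of treatment difference". The primary ITT analysis "will be conducted using all patients, as randomized". Choosing surgery in the AM arm is defined as rejecting the allocation, and its frequency is tracked separately from complete withdrawal.
- **Table 3** makes ipsilateral invasive cancer an event without condition and has no censoring row for elective surgery.

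**The concern.** The censoring rule for the primary endpoint depends on what withdrawal means in one sentence. A programmer working from 10.7 would find a withdrawal date for each AM woman who chose surgery, followed at once by an instruction to censor at withdrawal dates. No sentence says that these women are exempt, or that invasion found at such an operation is an AM event.

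This matters because invasion found at surgery is the main expected event in the surgery arm: Section 2.1 puts upstaging there at 10%, which is also the whole 2-year rate assumed in 10.2. If the AM withdrawal date precedes the pathology result, the same finding is counted in one arm and censored in the other. If the two dates coincide, the event is kept, but women whose operation shows no invasion still leave the risk set. Either way the censoring is tied to the operation and applies to one arm only, since 10.7 gives no such date to surgery-arm women who decline surgery.

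**Working it through.** **The plan's own figure.** With 10% in both groups, margin 5 points, one-sided alpha 0.05 and 80% power (10.2): n = 0.18 × (1.645 + 0.842)² / 0.05² = 445.1, rounded up to 446 per group. This reproduces and is not in dispute.

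**Inputs.**
- p, true AM 2-year rate: 10% (planning value), or 15% (at the margin).
- s, share of AM women operated on without documented invasion: the documents give no figure; 5-15% is assumed.
- u, share of those operations showing invasion: 0-20%, the published range in Section 1.6, which refers to initial excision.
- Women whose operation shows no invasion are assumed to have no event by 2 years.

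**Reading 1: only true study withdrawals are censored.** All events count and the ITT shift is zero.

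**Reading 2: 10.7 applied literally.** Kaplan-Meier then estimates the following.
- A. Withdrawal date before pathology, surgery spread evenly over 2 years. With e = p − su, the estimate is 1 − (1 − e − s)^(e/(e+s)).
- B. Withdrawal date before pathology, surgery early: (p − su)/(1 − s).
- C. Same date, event kept, even timing. With c = s(1 − u), the estimate is 1 − (1 − p − c)^(p/(p+c)).
- D. Same date, event kept, surgery early: 1 − (1 − su)(1 − (p − su)/(1 − s)).

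Shift in the AM estimate at p = 10%, in percentage points (s = 5% / s = 15%):

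| Case | u = 0 | u = 10% | u = 20% |
|---|---|---|---|
| A | +0.27 / +0.87 | -0.25 / -0.77 | -0.76 / -2.40 |
| B | +0.53 / +1.76 | 0 / 0 | -0.53 / -1.76 |
| C | +0.27 / +0.87 | +0.24 / +0.77 | +0.21 / +0.68 |
| D | +0.53 / +1.76 | +0.45 / +1.35 | +0.38 / +0.99 |

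Worked example, A with s = 15% and u = 20%: e = 0.10 − 0.03 = 0.07; 1 − 0.78^(0.07/0.22) = 7.60%, a shift of -2.40. A simulation of 400,000 women gave -2.42. The shift changes sign at u of about 5% in A and at u = p in B.

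**False non-inferiority at a true 15% versus 10%.** SE = √[(0.10 × 0.90 + 0.15 × 0.85)/446] = 2.21 points, and the probability is Φ(−1.645 − shift/SE), with the shift recomputed at p = 15%. This holds the SE fixed, so it is an approximation. Results against a nominal 5% (s = 5% / s = 15%):

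| Case | u = 0 | u = 10% | u = 20% |
|---|---|---|---|
| A | 3.4% / 1.2% | 5.5% / 6.6% | 8.6% / 22.3% |
| B | 2.3% / 0.2% | 3.9% / 2.0% | 6.4% / 10.7% |
| C | 3.4% / 1.2% | 3.5% / 1.5% | 3.7% / 1.7% |
| D | 2.3% / 0.2% | 2.5% / 0.4% | 2.8% / 0.8% |

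At u = 10%, the plan's own upstaging value, every entry is near nominal or conservative. The 22% figure needs case A with both s and u at the top of their ranges.

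**The case against.** The strongest reply is that 10.7 does not say these women are censored. The censoring sentence has its own condition, withdrawal from the study, and the paragraph opens by naming withdrawal and surgery as alternatives. There is also a reading that reconciles the text: 5.2.2.1 makes continued follow-up optional after such surgery, so a withdrawal date is needed for women who decline it. Section 10.2 points the same way throughout, and its planned analysis of the effect among compliers, which follows the randomization, would make little sense if every AM woman who crossed to surgery were censored at crossing. A statistician working from 10.2 would probably not censor.

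Most of this stands. It rules out calling the plan flatly contradictory, and it makes the harmless reading the likelier one. It does not settle the matter: no sentence excludes the literal reading, and the phrase in question is the one that triggers censoring a paragraph earlier.

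It is also fair to object that the size rests on assumptions. The crossover share is not in the documents, and a larger share would widen the range in both directions. Nor do the documents say that the withdrawal date would be the decision date, which is what losing events requires.

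**Conclusion.** Section 10.7 is ambiguous on a rule that governs the primary endpoint and, read literally, conflicts with the ITT plan. On the reading that the rest of the plan favours, the effect is nil. Applied literally, with s = 5-15% and u = 0-20%, it moves a 10% AM estimate by about +1.8 to -2.4 points if events are lost and by +0.2 to +1.8 points if they are kept. False non-inferiority at the margin is then about 0.2% to 22%.

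A reader might infer that the plan censors crossovers and so tilts the trial toward declaring AM non-inferior. The documents do not support that. They do not clearly prescribe the censoring, and its direction depends on how the date is recorded, when surgery occurs and how often invasion is found. The case for correcting the text is that the primary result should not depend on how one phrase is read or which date a site enters. The correction should be made, although the size of any effect is uncertain.

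**What to change.** In 10.7, for AM women who have surgery without documented invasion, replace the date of and reason for withdrawal with the date of surgery and the reason for the change in management. Then state that:

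1. Such surgery is neither study withdrawal nor a censoring event.
2. Invasion found at it is an ipsilateral invasive event in the ITT analysis, dated by the same rule as invasion found at surgery in the surgery arm.
3. Apart from the death rules in Table 3, early censoring applies only on withdrawal of consent for all follow-up or on loss to follow-up. The word ‘all’ matters: women who move to the Survival Follow-up Phase still have disease progression collected and should not be censored on entering it.

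Correct the pointer in 5.2.2.1 from Section 11.2. The intended target is most plausibly 10.2, which also speaks of declining the randomized arm.

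The cost is a few sentences and one cross-reference. The sample size is unchanged and no new data are needed, because 6.1.2 already records the change in management and its reason. Withdrawal dates already entered for this reason need checking.
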